12.4.2 Periodic Site Visits

Periodic on-site monitoring visits will be made to ensure adherence to all applicable regulations, including:

- The investigator’s adherence to the investigational plan,
- Appropriate informed consent practices,
- The accurate completion of all required case report forms,
- The accurate completion of all queries,
- The complete and accurate reporting of all adverse events,
- The maintenance of current IRB/EC approval and submission of required study progress reports to the IRB/EC,
- The maintenance of records and reports,
- The resolution of any study management issues.

The study monitor(s) will be responsible to complete a review of source documents for accuracy, completeness, and legibility. At a minimum, it is recommended that corresponding eCRFs be completed in EDC and ready for monitoring according to the time frames below.

Table 16: eCRF Completion

eCRF	Recommended Completion Time
Enrollment Form	Within 24 Hours
Index Procedure Forms (baseline through discharge)	Within 14 Days
7 day Phone Call	Within 7 Days
30, 90, 180 & 365 Day eCRFs	Within 14 Days
Serious Adverse Event Form	Fax Within 24 Hours
Device Performance Form, if a failure mode noted	Within 24 Hours
Study Exit Form due to AE or Lost to F/U	Within 72 Hours
Other Forms (Protocol Deviation, AE Narrative Summary, etc.)	Within 14 Days
Event Recorder	Within 14 Days
Holter Monitor	Within 14 Days

12.4.3 Clinical Monitor Reports

Site monitoring visits will be documented in a written monitoring report, prepared by the Sponsor's Clinical Monitor(s), or Sponsor's designee. Monitoring reports will include the progress of the study and identification of any follow-up activities or concerns from review of the subject records, study management documents, and informed consent forms. Resolution of concerns and completion of assigned tasks will also be documented in the monitoring report. A summary of the report will be given to the investigator in the form of a follow-up visit letter.

12.4.4 Final Monitoring Review and Study Closeout

A close-out or final visit will be conducted at each site. Any ongoing responsibilities will be discussed with the investigator and the investigation site personnel. A final monitoring report will be completed. A study closure letter will be sent to the investigator indicating the status of the study. It is the responsibility of the investigator to inform the Institution's IRB/EC in writing with the submission of the closure letter.

13.0 Ethical Considerations

13.1 Human Subjects Protection

The study will be performed in accordance with the relevant parts of the ICH Guidelines for GCP, 21 CFR 812, 50 and 56, and the Declaration of Helsinki.

Sponsor and Investigator will comply with applicable sections of ISO 14155:2011 and any regional or national regulations, as appropriate.

Investigator will not begin the clinical investigation until Investigator obtains the required written approval or favorable opinion from the IRB/ EC or regulatory authority, if appropriate.

Investigator will follow any additional requirements imposed by the IRB/EC or regulatory authority, if appropriate.

Sponsor will provide insurance for subjects, if required by national regulations.

13.2 Emergency Actions

Hansen Medical accepts the right of the investigator to deviate from the protocol in an emergency when necessary to safeguard the life or the physical well-being of a study subject. The investigator must give notice of any emergency deviations and justification for the deviation to the study personnel responsible at Hansen Medical and the IRB/ EC as quickly as possible after the episode, in any event no later than 5 working days after the emergency.

13.3 Amending the Protocol

This protocol is to be followed exactly. If needed, Hansen Medical must write amendments in order to alter the protocol. If any changes are required that affect the rights, safety, or welfare of the subjects or the scientific soundness of the study plan, they will be submitted to FDA as an

amendment or supplement to the IDE. Upon approval by the FDA, submission to each IRB/EC will occur.

No amendment to the protocol can be implemented before achieving all regulatory approvals, as per country specific regulations.

13.4 Study Termination

Hansen Medical, the US FDA and/or the European EC have the right to terminate this study at any time and remove all study materials from the site. A study may be terminated for any of the following reasons:

- Unsatisfactory rate of subject enrollment or compliance to eligibility criteria.
- Repeated noncompliance with the investigational plan.
- Inaccurate, incomplete, and/or untimely submission of data.
- The rate or severity of adverse events in the Hansen study or other similar studies indicates a potential health hazard to the subjects caused by the device.

14.0 Publication Policy

Sponsor will limit its review to a determination of whether Confidential Information is disclosed and shall not attempt to censor or in any way interfere with presentation or conclusions beyond the extent necessary to protect Confidential Information, to allow Sponsor to protect its rights in patentable or copyrightable material, and to check for technical correctness of Sponsor information. When reasonably requested by Sponsor, Institution and Principal Investigator will delay publication up to an additional 60 days to allow Sponsor to protect its rights in patentable or copyrightable material.

15.0 Study Definitions

AF Episode: An episode of AF 30 seconds or longer in duration on Holter or Trans-telephonic Monitoring (TTM), or 10 seconds in duration on 12-lead ECG.

Atrial Tachyarrhythmia Episode: An episode of atrial tachycardia, tachyarrhythmia (atrial fibrillation, atrial flutter or atrial) 30 seconds or longer in duration on Holter or Trans-telephonic Monitoring (TTM), or 10 seconds in duration on 12-lead ECG.

Blanking period: 90 day period between the index ablation procedure and the continuation of the 12 month follow-up period. If a subject is symptomatic during the 90 day blanking period, he/she may be placed on a previously ineffective Anti arrhythmic Drug (AAD). If a subject remains symptomatic, the AAD dose may be increased, a new AAD added, or the subject may be treated again using the Hansen System up to two more times before day 90. At the 90 day visit, subject will need to discontinue any class I, class II, class III and class IV AADs or maintain AAD's that were ineffective at baseline, at a dosage level less than or equal to the maximum baseline dosage. Calcium channel and beta blocker medications may continue for uses other than an antiarrhythmic drug.

Bleeding: A Major Complication of AF ablation if it requires and/or is treated with transfusion or results in a 20% or greater fall in HCT.

Discontinued Subjects: Subjects in whom the ablation catheter was inserted but did not undergo ablation or attempted ablation (no RF energy applied). Subjects are considered ‘discontinued’ if ablation was not possible due to non-study equipment failure or if their arrhythmia was determined to be a non-study arrhythmia (e.g. atrial flutter). These subjects will be followed for 7 days for safety endpoint evaluation.

Enrollment: Subject is considered to be enrolled once they have signed the informed consent form.

Paroxysmal AF: An atrial fibrillation where a subject has two or more spontaneously terminating episodes of atrial fibrillation that last longer than 30 seconds and shorter than seven days.

Screening Failure: Subject is excluded from enrollment from the study if they do not meet 1 or more of the pre-operative inclusion/exclusion criteria.

Symptomatic AF: Symptoms of AF that were experienced by the subject, made them seek medical attention, and were concurrent with a documented episode by ECG, event monitor and/or Holter monitoring. Symptoms may have included palpitations, irregular, rapid or slow pulse, dizziness, weakness, chest discomfort and breathlessness.

Appendix A Adverse Event Definitions

In addition to the definitions of Major Complications provided in **Appendix L** of the protocol, the following definitions apply to expected adverse events that may occur and must be reported throughout this clinical study. Events reported should represent a new onset or increase in the severity of the condition from the time of enrollment (the subject is considered to be enrolled at the time of the procedure).

A. SYSTEMIC COMPLICATIONS	DEFINITION
Allergic reaction (to contrast, drugs, anesthesia)	Allergy symptoms include but are not limited to: eye or skin redness, hives, rash, eye or skin itch, swelling, difficult breathing, respiratory arrest, sudden death.
Fever	Oral temperature > 101°F
Infection	The invasion of the body by pathogenic microorganisms and their multiplication which can lead to tissues damage and disease requiring treatment, e.g. endocarditis, pericarditis, sepsis.
Sepsis	Systemic infection with confirmed positive blood cultures.
Low Blood Pressure	Any blood pressure that is below the normal expected for an individual and has accompanying symptoms of hypo-perfusion (confusion, light-headedness, dizziness, syncope, etc.)
Ischemia/infarction of tissue/organ	Decrease blood supply to body tissue due to obstruction of blood flow.
Other Systemic Complications	Any new or exacerbated significant systemic complication that causes clinically relevant changes in the subject's health for which medical attention is required.

B. CARDIO-PULMONARY	DEFINITION
Angina/coronary ischemia	Chest, neck, arm, back, or other pain related to decreased coronary blood flow.
Arrhythmias	The development of a new atrial and/or ventricular arrhythmia or significant increase in the severity of a preexisting arrhythmia, that requires intervention or results in the signs and symptoms of vital organ hypoperfusion, such as dizziness, lightheadedness, or syncope, or any episode of cardiac arrest.
Atrial/Septal defect requiring repair	Defined as a significant residual atrial septal opening. Reported as clinically significant if intervention is performed for the primary purpose of repairing the ASD. If cardiac surgery is indicated for reasons other than residual ASD and the ASD is repaired at the same time, this does not meet the definition of clinically significant ASD.
Cardiac Arrest	Sudden cessation of heartbeat and cardiac function, resulting in the loss of effective circulation.
Congestive Heart Failure	Failure of the heart to pump blood with normal efficiency. Development of an acute episode of or exacerbation of existing low cardiac output or fluid overload accompanied by peripheral and/or pulmonary edema.
Endocarditis	Inflammation of the endocardium. Left untreated can cause systemic emboli and cardiac valve dysfunction.
Damage to heart valves and / or supporting structures	Defined as damage to a heart valve or supporting structure which requires intervention as a result of damage.
Dyspnea	New onset or increasing episodes of shortness of breath.

B. CARDIO-PULMONARY	DEFINITION
1 st and 2 nd degree heart block not requiring treatment	New onset 1st or 2nd degree heart block not requiring treatment.
Hemoptysis	Coughing up blood.
Need for a permanent pacemaker	Bradycardia rhythm that becomes chronic (lasting more than a few days), results in intolerable symptoms or is believed to be irreversible requiring implantation of a permanent pacemaker.
Perforation of cardiac muscle	Perforation of the heart muscle requiring additional treatment (including efforts to seal the perforation or pericardial drainage), or resulting in significant pericardial effusion, tamponade, myocardial infarction, or death.
Pulmonary Hypertension	Increased pressure in the pulmonary vessels eventually leading to heart failure. Symptoms can include chest pain (frontal), dyspnea with activity, lightheadedness with activity, dizziness, fatigue, weakness.
Pulmonary vein obstruction	An obstruction in the pulmonary vein that can decrease blood flow to the atria.
Pleurisy	Pleurisy is an inflammation of the pleura often causing symptom of stabbing pain in the chest aggravated by breathing, chest tenderness, cough, and shortness of breath. Often associated with a pericardial rub heard on auscultation.
Respiratory Arrest	Sudden complete cessation of respiratory movement.
Ventricular fibrillation	An abnormally rapid heart rhythm that originates from a ventricle where the ventricles beat rapidly in a chaotic, purposeless fashion not allowing the heart to pump blood effectively to the body.
Other Cardio-Pulmonary Complications	Any new or exacerbated significant cardiac or pulmonary complication that causes clinically relevant changes in the subject's health for which medical attention is required.

C. VASCULAR COMPLICATIONS	DEFINITION
Air Embolism	Obstruction of the circulation by air that has gained entrance to a blood vessel(s).
Aneurysm	Localized widening (dilatation) of an artery, vein, or the heart. At the area of an aneurysm, there is typically a bulge and the wall is weakened and may rupture.
Atrio-venous fistula	Formation of an abnormal connection between the lumens of an artery and a vein as documented by CT, ultrasound, angiography, or direct observation.
Access site discomfort	Pain and/or tenderness at the access site.
Bleeding	Bleeding requiring observation resulting in prolonged hospitalization and/or transfusion and/or treatment other than applying pressure & bandage.
Hematoma	A mass of usually clotted blood that forms in tissue, organ or body space as a result of leakage from a blood vessel that requires additional treatment beyond applying pressure.
Retroperitoneal hemorrhage	Bleeding into the retroperitoneal space. RPH is often associated with femoral artery sheath placement superior to the inferior epigastric artery resulting in vessel perforation.
Perforation or rupture of a blood vessel	Defined as perforation in an access vessel wall or the aorta confirmed by extravasations of contrast under fluoroscopy.

C. VASCULAR COMPLICATIONS	DEFINITION
Pseudoaneurysm	Enlargement of the aorta, iliac, or femoral arteries, which contain some or all of the medial layer, the adventitia, and periaortic tissue most commonly associated with previous aortic operative procedures, trauma, and/or infection. Pseudoaneurysms typically present as a well-defined collection of blood outside the vessel wall from contained rupture.
Temporary or total occlusion of an artery	Vessel lumen narrowing or obstruction by atherosclerotic plaque, thrombus, or embolism causing a decrease or occlusion of blood supply to the extremities.
Thrombophlebitis	Inflammation of a vein that occurs when a blood clot forms.
Vessel Spasm	A sudden constriction of a vessel limiting blood flow downstream.
Other Access site complications	Any new or exacerbated significant vascular complication that causes clinically relevant changes in the subject's health for which medical attention is required.

D. NEUROLOGIC COMPLICATIONS	DEFINITION
Change in Mental Status	A delirium or acute confusional state associated with a disturbance in cognition, mood, attention, arousal, and self-awareness, as evidenced on clinical assessment, which arises acutely, either without prior intellectual impairment or superimposed on chronic intellectual impairment.
Femoral Neuropathy	Pain and numbness in the anterior thigh associated with quadriceps muscle weakness and decreased patellar reflex lasting > 1 month after treatment.
Nerve Injury/Peripheral Neuropathy	Direct damage to nerves surrounding the access site, operative field, and the resultant signs and/or symptoms of such damage.
Other neurologic complications	Any new or exacerbated significant neurologic complication that causes clinically relevant changes in the subject's health for which medical attention is required.

E. OTHER COMPLICATIONS	DEFINITION
Headache	Headache lasting >24 hours and/or not relieved by pain medication.
Heparin induced thrombocytopenia (HIT)	Development of thrombocytopenia (low platelet counts) due to the administration of Heparin. It predisposes to thrombosis, the formation of abnormal blood clots inside a blood vessel.
Renal Insufficiency	Slowly progressive failure of renal function resulting from some disease, e.g., diabetes, cancer, hypertension, glomerulonephritis, that causes gradual destruction of the kidneys, or if creatinine levels are available, an increase of > 25% above the pre-procedure creatinine level.
Renal failure	Defined as a new need for dialysis or a creatinine increasing to 3.5 mg/dL or greater. Not included as Renal Failure is any Renal Dysfunction defined as an increase of creatinine over 1.0 mg/dL over the baseline.
Surgery required for treatment of an Adverse Event	Emergent or Urgent surgery required to treat an adverse event.
Increased exposure to radiation	Radiation exposure resulting in symptoms consistent with overexposure to radiation.
Other possible adverse effects	Any new or exacerbated significant complication that causes clinically relevant changes in the subject's health for which medical attention is required.

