Prior to the start of any ablation procedure, the subject's echocardiogram will be reviewed to ensure no evidence of left atrial thrombus. A routine EP study may be performed to evaluate the location, morphology, and dimensions of each pulmonary vein by venogram. Intra-cardiac echocardiography (ICE) may also be performed prior to the ablation procedure at the physician's discretion.

A subject is required to meet all the inclusion and none of the exclusion criteria to participate in the study. Enrollment occurs when a subject signs the Informed Consent Form. The subject must then meet all additional intra-procedural enrollment criteria (i.e. no intramural thrombus, etc.). If the subject does not meet all intra-procedural enrollment criteria, the subject will not be treated with the study device and will be withdrawn from the study. The screening, baseline, and withdrawal case report forms should be completed. The investigator shall report any acute procedural adverse events on the adverse event form.

These subjects who are withdrawn prior to the procedure will count against the maximum enrollment limit. However, the company requests that the maximum enrollment limit is increased accordingly to account for those who signed the Informed Consent Form but did not undergo the study procedure.

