5.2 Primary Safety Endpoints

The primary safety endpoint is defined as the incidence of Major Complications, as defined below:

Major Complications during the procedure through 7 days:

- Death
- Stroke
- Myocardial Infarction
- Diaphragmatic paralysis
- Transient Ischemic Attack (TIA)
- Cardiac Tamponade
- Pericarditis
- Pneumothorax
- Hospitalization or Emergency Room Visit
- Vascular Access Complication
- Heart Block
- Pulmonary Edema
- Pericardial Effusion resulting in pericardiocentesis or surgical intervention
- Thromboembolism

Major Complications during the procedure through 180 days:

- Pulmonary vein stenosis
- Atrio-esophageal fistula

Major Complication definitions can be found in **Appendix L** of this protocol. All Major Complications, as reported by the clinical investigator, will be reviewed and adjudicated by the Clinical Events Committee (CEC).

All adverse events will be documented and collected once the informed consent has been signed.

In the event of a study subject death, all possible efforts will be made to obtain relevant records from the hospital or the subject's primary care physician, including death certificates, to determine the cause of death.

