7.3.1 Screening/Baseline Evaluation – within 30 days of enrollment

The following baseline data must be collected from all subjects prior to enrollment in the study. Subjects will be screened for eligibility by the investigator or designee. Subjects who meet the eligibility criteria for participation will be required to read and sign an Informed Consent Form prior to baseline evaluation. A medical history inclusive of medications will be taken and a physical examination will be performed to assess overall physical status.

Test results that are within the timeframes specified below may be used even though the actual test was done prior to the subject's informed consent. This may be done only for standard of care tests with the intent to minimize stress and discomfort to the subject and reduce costs. Required screening evaluations include the following.

The following evaluations will be conducted at the baseline visit:

- Inclusion/Exclusion criteria assessment,
- Informed consent,
- Demographics,
- Medical history,
- Medication history: Antiarrhythmics (2 years); Anti-platelets & Anticoagulation (3 months),
- Physical examination,
 - Vital signs,
 - New York Heart Association (NYHA) Class (see **Appendix E**),
- Laboratory evaluations,
 - CBC,
 - INR (only if subject previously on anticoagulation therapy),
 - Serum Creatinine,
 - Blood Urea Nitrogen (BUN),
 - Pregnancy test (women of child bearing potential) – ***within 7 days of procedure***,
 - If a subject become pregnant during this study, she must notify the site staff
- TTE to assess cardiac structure, function, LA size and EF (***within 3 months prior to procedure***),
- ***CT or MR (within 3 months prior to procedure)*** to evaluate pulmonary vein and left atrial morphology and dimensions.

Note: If a CT or MR is performed at baseline, the same imaging specifications performed at baseline must be performed at the follow-up visit for 180 and 365 day.

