7.3.2 Pre-Procedure Evaluation – Within 24 hours of procedure

Within 24 hours prior to the initial ablation the following will be done:

- Blood will be drawn to measure for INR value*,
- 12-lead electrocardiogram (ECG) performed to check for cardiac rhythm and indication of myocardial ischemia,
- TEE/ICE should be performed to assess for possible atrial thrombus 24 hours prior to procedure or the day of the procedure. Also to establish that thrombus, cardiac structure, function, LA size and EF meet protocol criteria.

**If subject's INR is minimally >3.0 within 24 hours pre-procedure, another INR may be done on day of procedure, if INR results < 3.0, subject may be enrolled.*

Table 8: Definition of Study Time Points

Interval	Time Point and Window (if applicable)
Screening/Baseline	Within 30 days except for pregnancy test (within 7 days), from initial ablation
Pre-procedure	Within 24 hours prior to the initial ablation.
Enrollment	Subject is considered to be enrolled once they sign the Informed Consent Form.
Discharge	0 – 48 hours or prior to discharge; whichever comes first.
7-Day Follow-up	7 days \pm 3 days.
30-Day Follow-up	30 days \pm 14 days post initial ablation procedure.
90-Day Follow-up	90 days \pm 14 days post initial ablation procedure.
180- Day Follow-up	180 days (6 months) \pm 30 days post initial ablation procedure.
365- Day Follow-up	365 days \pm 30 days post initial ablation procedure.

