7.8 Adverse Events

Adverse events (AEs) are defined as any unfavorable and unintended sign, symptom, or disease possibly associated with the study procedure, study device or required study testing. This does not imply that there is a relationship between the adverse event and the device under investigation. All AEs will be recorded onto the Electronic Data Capture (EDC) case report form for visits (post procedure) documented in the permanent medical record. The investigator is ultimately responsible for reporting AEs to the Sponsor. The investigator will evaluate the AE in detail, including the date of onset, description, severity, duration, outcome, and causality as specified in this section.

Intensity or Severity of an Adverse Event:

The intensity or severity of each AE must be assessed according to the following classification:

Table 10: Adverse Event Severity

Mild	An event that results in minimal transient impairment of a body function or damage to a body structure, and/or does not require intervention other than monitoring.
Moderate	An event which results in moderate transient impairment of a body function or damage to a body structure, or which requires intervention, such as the administration of medication or cardioversion, to prevent permanent impairment of body function or damage to body structure.
Severe	An event which is life threatening, which results in a permanent impairment of a body function or damage to a body structure, or which requires significant intervention, such as the major surgery, to prevent permanent impairment of body function or damage to body structure.

Outcome:

The outcome of each AE must be assessed according to the following classification:

Table 11: Adverse Event Outcome

Resolved	Subject fully recovered with no observable residual effects.
Improved	Subject's condition improved, but residual effects remain.
Unchanged	AE is ongoing.
Worsened	Subject's overall condition worsened.
Death	Subject died as a result of the AE (whether or not the AE is related to the investigational device or procedure).

Causality:

The causality of each AE must be assessed according to the following classification:

Table 12: Adverse Event Causality

Device –related	The investigational device directly caused or contributed to the AE.
Possibly device related	The investigational device may have caused or contributed to the AE.

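### Adverse-event collection starts at consent in Section 5.2 but at the procedure in Appendix A, Table 9 and Section 7.8, so non-serious harm from pre-ablation study tests can go unreported

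*Protocol*

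**What the plan says.** Three places in the protocol put enrollment at consent. Section 5.0: "Enrollment occurs when a subject signs the Informed Consent Form". Table 8: "Subject is considered to be enrolled once they sign the Informed Consent Form". Section 15.0: "Subject is considered to be enrolled once they have signed the informed consent form". Section 5.2 starts safety collection at the same moment: "All adverse events will be documented and collected once the informed consent has been signed". Section 7.8 defines an adverse event broadly enough to cover the work-up, as something "possibly associated with the study procedure, study device or required study testing".

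Three places start later. The opening paragraph of Appendix A asks for events that are new or have worsened since enrollment, and explains in a parenthesis that "the subject is considered to be enrolled at the time of the procedure". Table 9 leaves the adverse-event row empty under Screening/Baseline and Pre-Procedure and marks it from Procedure onward. Section 7.8 places the recording of events at visits, with a post-procedure qualifier.

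Some other text also treats enrollment as later than consent. Under Section 7.3.1, eligible subjects "will be required to read and sign an Informed Consent Form prior to baseline evaluation", yet the same section wants the baseline data in hand before enrollment. Section 15.0 says of a screening failure: "Subject is excluded from enrollment from the study if they do not meet 1 or more of the pre-operative inclusion/exclusion criteria". Section 6.7 puts every subject who signed consent in the ITT population, then describes those who fail an intra-procedural criterion as not enrolled.

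**The concern.** Two start points for adverse events cannot both be followed. The interval between them contains study-required tests that carry their own risks: a CT or MR at baseline, and a TEE or ICE shortly before ablation. The first event type that Appendix A defines is an allergic reaction, with contrast as a named cause. If such a reaction follows a baseline CT done after consent, Section 5.2 collects it and Section 7.8 counts it as an adverse event. Under Appendix A it predates the onset reference, and Table 9 gives it no column.

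At stake is the completeness and comparability of the general adverse-event listing, which Sections 5.5 and 6.7 name as an analysis. Sites that follow Section 5.2 would report these events and sites that follow the schedule table would not. A difference between sites could then reflect which page the coordinator reads.

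**Working it through.** No figure in the protocol decides the main point, so the check sets the rules side by side and traces event types through them.

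| Place in protocol | Start point |
|---|---|
| 5.2 | Signed consent |
| 5.0, Table 8, 15.0 (enrollment) | Signed consent |
| 7.8, definition | Includes harm from required tests, so reaches back before ablation |
| 7.8, recording | Post-procedure visits |
| Appendix A, onset | Enrollment, set at the procedure |
| Table 9, adverse-event row | Procedure column |

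Tracing cases through these rules:

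1. Baseline CT done as standard of care before consent, which 7.3.1 permits. A reaction is outside collection under either start point. No conflict.
2. Baseline CT done after consent, with a non-serious contrast reaction. In under 5.2 and the 7.8 definition; out under Appendix A, Table 9 and the 7.8 recording sentence. Conflict.
3. TEE or ICE done after consent in the 24 hours before the procedure, with a minor injury. Same as case 2. Conflict.
4. TEE or ICE done at the onset of the procedure, as the synopsis note and Table 9 footnote 5 allow. It falls in the Procedure column. No practical conflict.
5. A serious event between consent and ablation. Section 7.8.2 requires all serious adverse events to be reported within 24 hours and sets no onset condition. It should be reported.
6. A TIA between consent and ablation. TIA is on the Major Complication list in 5.2, and those definitions sit in Appendix L, which Appendix A supplements. The Appendix A onset sentence is therefore not clearly its rule, and the primary endpoint window in 5.2 runs from the procedure.

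Only cases 2 and 3 are lost. The affected group is the subjects with a required test after consent and before the procedure. The protocol does not say how many that is; the 125 to 250 planned subjects are an upper bound.

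The word enrolled also drives the interim trigger, so I checked how far the two meanings differ in number. Section 6.5 gives 5% withdrawn before the procedure.

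- Counting consents: 125 × 0.95 = 118.75, about 119 treated at the first look; 250 × 0.95 = 237.5, about 238 at the maximum.
- Counting treated: 125 / 0.95 = 131.6, so 132 consents; 250 / 0.95 = 263.2, so 264 consents.

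To size this I used a fixed-sample rule with a Beta(1,1) prior, independent endpoints, the 95% posterior thresholds of 6.1 and 6.2, and the true rates of 6.5 (8% safety, 72% effectiveness).

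- n = 250: joint power 99.0%, close to the 98% stated for the adaptive design. The 98% itself cannot be reproduced, because the prior and prediction model are in Appendix M, which is not at hand.
- n = 125: success needs at most 13 safety events and at least 77 effectiveness successes; 0.8737 × 0.9955 = 0.870.
- n = 119: at most 12 and at least 74; 0.8437 × 0.9923 = 0.837.
- n = 238: 98.4%.

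The difference is about 3 points of fixed-sample power at the first look (87.0 − 83.7 = 3.3) and under 1 point at the maximum (99.0 − 98.4 = 0.6).

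**The case against.** The best defence is that Section 5.2 states the consent rule plainly, that the Appendix A wording is a parenthesis, and that a careful site would follow the body text. That would carry weight if the parenthesis stood alone. It does not: the schedule table and the recording sentence in 7.8 point the same way, and a schedule table is what coordinators commonly work from.

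It is also fair to say that the exposure is limited. Tests may predate consent, TEE or ICE may be done at the start of the procedure, serious events have their own rule, and the primary cohort is treated subjects with a safety window that opens at the procedure. All of that stands and limits the point to non-serious events in part of the sample.

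A reader might go further and infer that the 125-subject trigger and the Table 7 site caps are themselves counted by conflicting rules. The documents do not support that strongly. Section 5.0, Table 8, Section 15.0 and the ITT definition favour counting consents. Section 5.0 expressly counts subjects withdrawn before the procedure against the maximum and asks for the limit to be raised to compensate. The Appendix A parenthesis concerns event onset, not counting. The screening-failure wording can be read as covering people ruled out before they sign, since Sections 9.3 and 10.2.1 place an eligibility judgement before consent. Appendix M may also fix the counting unit. What remains is loose wording in 15.0, 7.3.1 and 6.7, worth tidying but not evidence of a faulty trigger.

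**Conclusion.** The contradiction is real and is in the current text: adverse-event collection begins at consent in one section and at the procedure in three other places. The consequence is possible under-reporting of non-serious harm from study-required tests between consent and ablation, in those subjects whose tests fall in that interval. The protocol gives no figure for their number.

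Two larger inferences should be resisted. The gap does not reach every subject, for the reasons traced above. It also does not materially alter the primary safety result. The effect of the enrollment wording on sample size is modest at the stated 5% withdrawal: about 119 rather than 125 treated at the first look. The power comparison rests on an assumed flat prior, independent endpoints and a fixed sample size, and the adaptive design can continue enrolling after that look.

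This should be corrected because the cure is nearly free and gives every site one start point.

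**What to change.** In Appendix A, replace the parenthesis so that onset or worsening is dated from the time informed consent is signed. In Table 9, start the adverse-event row at Screening/Baseline and mark Pre-Procedure as well. In Section 7.8, remove the post-procedure restriction on recording.

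For consistency, define a screening failure in Section 15.0 as a consented subject who fails a pre-operative criterion. Reword Section 7.3.1, where baseline data are required before enrollment, and Section 6.7, where consented subjects are called not enrolled, so that both fit the consent definition.

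Leave the unit for the interim triggers and the Table 7 caps as it is. Moving it to treated subjects would reverse the counting rule in Section 5.0 and could disturb the design described in Appendix M, for a small gain.

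The cost is protocol wording and two cells of one table, plus a few more pre-procedure events to record.
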